- d: To be performed at EOT or at ET. EOT is defined as when the subject is released from the CRU following completion of all assessments through Day 8. ET is defined as when the subject is released from the CRU if the subject terminates the study early. Vital Sign, ECG, and Safety laboratory results for serum chemistry, hematology, coagulation, and urinalysis are to be available for review by the PI or designee prior to subject release from the CRU at the EOT or ET visit.
- e: To be performed 7 days (\pm 2 days) following EOT or ET. End of Study (EOS) is defined as when the CRU contacts the subject by phone call 7 days (\pm 2 days) after EOT or ET visit to determine if any SAE or study drug related AE has occurred since the last study visit. All subjects who received LOXO-292 (including subjects who terminate the study early) will be contacted.
- f: Symptom-driven physical examination(s) may be performed at other times, at the PI's or designee's discretion. Scheduled abbreviated physical examinations will include, at a minimum, examination of respiratory, cardiovascular, and gastrointestinal systems, with the option for further examination of additional systems as necessary based on reported symptoms/AEs.
- g: Subjects are to be supine for 10 minutes prior to ECG assessment. ECGs will be obtained prior to and as close as possible to the scheduled blood draws if scheduled at the same time.
- h: Vital signs (HR, BP, and RR) will be obtained at Screening and C-I (Day -1), predose, at 2 hours (\pm 10 minutes) and 4 hours (\pm 10 minutes) postdose on Day 1, and once daily through EOT (or ET). Vital sign measurements should be carried out prior to and as close as possible to having blood drawn. BP and HR will be measured using the same arm for each reading. Subjects are to be supine for 5 minutes prior to vital signs assessments.
- i: To be performed within 2 hours prior to dosing on Day 1.
- j: Samples for serum chemistry will be obtained following a fast of at least 12 hours at Screening and at C-I (Day -1); at other scheduled times, serum chemistry tests will be performed after at least an 8-hour fast. However, in case of dropouts or rechecks, subjects may not have fasted for 12 or 8 hours prior to the time that the serum chemistry sample is taken.
- k: For subjects who may be anuric, urine samples for urinalysis will not be collected.

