11 STUDY DESIGN

11.1 Overall Study Design and Plan

This is a non-randomized, open-label, parallel-cohort, multiple-site, single-dose renal impairment study.

Screening of subjects will occur within 28 days prior to the first dosing.

On Day 1, subjects will receive a single oral dose of LOXO-292. Plasma and urine samples (if possible), will be taken predose and through 168 hours for healthy subjects and subjects with RI for LOXO-292 PK assessment.

Assignment to a renal function panel will be as follows:

Cohort	Renal Function	eGFR (mL/min/1.73m ²) *
1	Healthy Matched Control	≥ 90 **
2	Mild	60 ≤ eGFR < 90
3	Moderate	30 ≤ eGFR < 60
4	Severe (not on dialysis)	< 30
	* eGFR based on MDRD equation at Screening. Baseline eGFR will be obtained for all subjects (i.e., subjects with RI and healthy matched control subjects) by taking the mean of the eGFR obtained from Screening and from historical values within a 3-month period from Screening. If no historical measurement is available, a second Screening eGFR sample will be taken during the Screening period (≥ 14 days apart) and the mean of the two values will be used as the Baseline eGFR for cohort assignment. Individual eGFR values recorded for each measurement contributing to the subject mean baseline value must fall within the specified eGFR ranges for each cohort (i.e., healthy, mild, moderate, and severe) to categorize subjects' renal impairment status.	
	** For healthy-matched control subjects, a single assessment of actual creatinine clearance computed over a 24-hour urine collection may be used in place of the eGFR (based on the MDRD equation), at the PI's discretion.	

Each healthy matched-control subject (Cohort 1) will be demographically matched (1:1) by age (\pm 10 years), body mass index (BMI; \pm 20%), and sex to the enrolled renal impairment subject(s). Should another renal impairment subject be identified with whom an already enrolled healthy subject is demographically matched, the healthy subject may also be matched with that impaired subject as long as the impaired subject is in a different renal impairment cohort. Each subject with normal renal function may be matched with up to 1 subject within each renal impairment cohort (i.e. mild, moderate, and severe).

Safety and tolerability will be assessed through EOT or ET by monitoring AEs, performing physical examinations, and clinical laboratory tests, measuring vital signs, and recording ECGs.

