14.2.6.2 Monitoring

Subjects will be monitored from Screening (signing of informed consent) until EOS (or ET if the subject discontinues and does not complete a follow up call) for adverse reactions to the study drugs and/or study procedures. At the EOT or ET visit, subjects will be asked how they are feeling prior to check out from the CRU. During the EOS/follow-up phone call, subjects will be queried with an open-ended question such as: 'How have you been feeling since your last visit?'.

AEs (whether serious or non-serious), including abnormal laboratory test value(s), abnormal vital signs, and ECG abnormalities deemed clinically significant by the PI or designee will be evaluated by the PI or designee and treated and/or followed through EOT or ET. AEs which are ongoing at the EOT or ET which are assessed as related to study drug by the PI (or designee) will be followed through the EOS. AEs which are ongoing at the EOS which are assessed as related to study drug may be continued to be followed until the symptoms or value(s) return to normal, or acceptable levels, as judged by the PI or designee and confirmed by the Sponsor.

Treatment of serious adverse events (SAEs) will be performed by a physician, either at the CRU or at a nearby hospital emergency room. Where appropriate, medical test(s) and/or examination(s) will be performed to document resolution of event(s). Outcome may be classified as death related to AE, not recovered or not resolved, recovered or resolved, recovered or resolved with sequalae, recovering or resolving, or unknown.

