14.2.6.3 Reporting

AEs and SAEs will be collected beginning at informed consent. AEs will be recorded throughout the study (i.e., from signing of the ICF until EOS or ET if the subject discontinues and does not complete a follow up call), either as subject medical history (if the event is reported as beginning prior to signing of the ICF or if the event occurs prior to study drug administration on Day 1 and is assessed as not related to study procedures by the PI [or designee]) or as AEs (if the event occurs after signing of the ICF but prior to study drug administration on Day 1 and is assessed as related to study procedures by the PI [or designee], or if the event occurs after study drug administration on Day 1 through EOT or ET regardless of relationship to study drug). From EOT or ET through EOS, only AEs assessed as related to study drug by the PI (or designee) are to be reported. All SAEs that develop from the time of ICF signing until EOS (or ET, if subject discontinues from the study and does not complete the follow up call) are to be reported.

Unless a subject withdraws consent or is withdrawn from the study and does not complete the follow up call, all subjects must be followed until the EOS. AEs which are ongoing at the EOS which are assessed as related to study drug by the PI or designee may be followed until the symptoms or value(s) return to normal or acceptable levels, as judged by the PI or designee and confirmed by the Sponsor. The PI (or designee) should use appropriate judgment in ordering additional tests as necessary to monitor the resolution of events. The Sponsor may request that additional safety tests be performed.

The PI or designee will review each AE and assess its relationship to drug treatment (yes [related] or no [unrelated]). Each sign or symptom reported will be graded on the National Cancer Institute (NCI) Common Terminology Criteria for Adverse Events (CTCAE) version 5.0 toxicity grading scale.

Grade refers to the severity of the AE. The CTCAE displays Grades 1 through 5 with unique clinical descriptions of severity for each AE based on the following general guideline ([NCI CTCAE 27 Nov 2017](#)):

Grade 1	Mild; asymptomatic or mild symptoms; clinical or diagnostic observations only; intervention not indicated.
Grade 2	Moderate; minimal, local or noninvasive intervention indicated; limiting age-appropriate instrumental ADL*.

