A TEAE is defined as an undesirable event not present prior to medical treatment, or an already present event that worsens either in intensity or frequency following the treatment. Each TEAE will be attributed to the treatment based on Investigator (or designee) judgment as well as on its onset date and time. If an AE has a change in severity grade, the original AE will be given a resolution date and time of the time of severity grade increase or decrease and a new AE record will be initiated with the new severity grade, and the new AE record will use the resolved date/time of the previous record as the onset date/time. If the severity grade of an AE remains the same, the AE will be kept open through to resolution.

If the onset date and/or time of an AE is/are missing, the AE will be treated as a TEAE, unless the onset date of the AE is known to have occurred prior to dosing. TEAEs will be tabulated by system organ class and preferred term. Summary tables will include the number of subjects reporting the AE and as a percent of the number of subjects dosed by cohort and overall. In addition, the number of AEs will be summarized. For an AE with multiple changes in severity, a new record with severity less or equal to its maximum severity will not be included in the adverse event summary tables. Tables will also be presented by severity grade and relationship to study drug. If a subject experienced the same TEAE at more than once with different level of severity grade, only the most severe one will be counted. Similarly, if a subject experienced the same TEAE more than once with different level of drug relationship, only the one most closely related to the study drug will be counted.

Should any serious adverse events (SAEs) occur during the study, the SAEs will be displayed in a table and a narrative included in the Clinical Study Report.

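### After EOT/ET, non-serious AEs are recorded only if judged related, yet the TEAE tables count them together with the earlier all-cause events

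*Protocol*

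**What the plan says.** Protocol 14.2.6.3 sets three rules, repeated in footnote l of the Section 7 flow chart.

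- After dosing, an event is an AE "if the event occurs after study drug administration on Day 1 through EOT or ET regardless of relationship to study drug".
- After that, the rule narrows: "From EOT or ET through EOS, only AEs assessed as related to study drug by the PI (or designee) are to be reported".
- Serious events are not narrowed. The rule covers "All SAEs that develop from the time of ICF signing until EOS", whatever the relationship.

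Footnote d fixes the switch point: "EOT is defined as when the subject is released from the CRU following completion of all assessments through Day 8". ET is the earlier release of a subject who stops. Footnote e places the EOS call 7 ± 2 days after EOT or ET. For that call, Section 14.2.6.2 says that "subjects will be queried with an open-ended question such as: 'How have you been feeling since your last visit".

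The protocol describes the period of safety assessment in two ways. Section 11.1 says: "Safety and tolerability will be assessed through EOT or ET by monitoring AEs". Section 11.1.1 adds the EOS call, and Section 14.2.6.2 monitors subjects until EOS.

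SAP 7.3 opens its definition with "A TEAE is defined as an undesirable event not present prior to medical treatment" and extends it to events that worsen after treatment. It sets no closing date. TEAEs are counted by cohort and overall, against all subjects dosed, and "Tables will also be presented by severity grade and relationship to study drug". The shells for Tables 12-1 and 14.3.1.1 to 14.3.1.4 have no period column and no footnote on how late events were captured. SAP 3 does say that the call looks for drug-related AEs and SAEs, but SAP 7.3 does not carry this into the tables.

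**The concern.** A TEAE table is normally read as every event with onset in the period it covers. Here the period is unstated and the entry rule changes partway through it. After EOT/ET, a non-serious event enters only if an unblinded investigator attributes it to the drug, so an unrelated late event cannot appear in any of these tables.

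This has two consequences. All-cause counts are incomplete if the tables are taken to run to EOS. The Related and Not Related columns of Tables 14.3.1.3 and 14.3.1.4 also lean towards Related, because in the late period a non-serious event can enter only the Related column. Safety and tolerability in subjects with renal impairment (RI) is a secondary objective and no safety inference is planned, so these descriptive tables are its main evidence.

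**Working it through.** The documents give no AE rate for this study, so there is no planned figure to reproduce. Step 1 needs no assumption, step 2 uses the schedule, and steps 3 to 5 are illustrations.

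**1. What can enter the tables**

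| Onset | Non-serious, related | Non-serious, unrelated | Serious |
|---|---|---|---|
| Dosing to EOT/ET | counted | counted | counted |
| EOT/ET to EOS | counted | cannot appear | counted |

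Nothing in SAP 7.3 separates the two rows.

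**2. Length of each period.** Dosing to the 168-hour procedures is 7 days, and the call follows 7 days later (range 5 to 9). For a completer the related-only part of post-dose follow-up is 7/14 = 50% (5/12 = 42% to 9/16 = 56%). After ET the all-cause part is shorter, but the subject stays in the denominator.

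**3. Size if event rates are constant.** Let r be the true related proportion of non-serious AEs and W the days from EOT to the call.

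- Recorded related proportion = r(7+W) / [r(7+W) + 7(1−r)]
- Events captured = [r(7+W) + 7(1−r)] / (7+W)

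For a range of r, Protocol 9.1.1 gives 2.6/12.4 = 21% (constipation) to 11.8/15.7 = 75% (fatigue). Those are patients with cancer in the ongoing Phase 1/2 study, so they only set a range. For r = 50% and W = 7: 7/(7 + 3.5) = 66.7% recorded as related, and 10.5/14 = 75.0% captured.

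| True r | Recorded as related, W = 5 / 7 / 9 | Events captured, W = 5 / 7 / 9 |
|---|---|---|
| 21% | 31.3 / 34.7 / 37.8% | 67.1 / 60.5 / 55.6% |
| 50% | 63.2 / 66.7 / 69.6% | 79.2 / 75.0 / 71.9% |
| 75% | 83.7 / 85.7 / 87.3% | 89.6 / 87.5 / 85.9% |

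**4. Size if related events stop at EOT.** With the half-life of about 24 hours in Protocol 9.2.1, 168 hours is 7 half-lives and 0.5^7 = 0.8% of drug remains. If no related event starts after EOT, the tables are simply the Day 1 to 8 tables plus any late SAEs. They are then right for that period and incomplete only as a statement to EOS. With r = 50% in the first week, unrelated events continuing at the same rate and W = 7, the tables show 50% related, against 3.5/(3.5 + 7) = 33% over the full period. They capture 7/10.5 = 67% of events.

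**5. Can it differ by cohort?** Assume a 10% weekly risk of a related event and a weekly risk u of an unrelated one. With two equal weeks, the share of subjects with any AE is 1 − (1−u)² × 0.9² under full recording and 1 − (1−u) × 0.9² under the current rule.

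- Equal risk, u = 20% in both groups: both fall from 48.2% to 35.2%, and the difference stays 0.
- Unequal risk, u = 30% in RI and 10% in healthy subjects: RI falls from 60.3% to 43.3% and healthy from 34.4% to 27.1%. The difference shrinks from 25.9 to 16.2 points, and the subjects missed per 8 are 1.4 and 0.6.
- Unequal attribution: let u = 20% in both groups, related events occur only in the first week, and a fraction q of late unrelated events be called related. The recorded share is 1 − 0.8 × 0.9 × 0.8^q, which is 31.1% at q = 0.2 and 35.6% at q = 0.5, against 42.4% under full recording. The gap of 4.5 points is 0.36 of a subject in 8.

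The documents give neither u nor q, so none of these cases can be confirmed.

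**The case against.** The strongest reply is that the rule is deliberate and disclosed. The synopsis, footnote e, Section 11.1.1 and SAP 3 all say that the call looks for SAEs and drug-related AEs. Narrowing collection after confinement is a legitimate choice, and with little drug left few related events should start so late. Tables 14.3.1.3 and 14.3.1.4 show counts and not a related percentage. Appendix 16.2.7.1 lists onset times, so a reader can separate the periods by hand. All of this stands, and it limits the size of the problem. It does not restore the unrelated late events, and the summary tables still do not state the rule.

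A reader might draw four stronger conclusions that the documents do not support.

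- **The rule biases the comparison between cohorts.** One rule and one nominal window apply to all four cohorts. A distortion needs different background rates, attribution or early termination. That is plausible in an open-label study of RI subjects and selected healthy controls, but no data support it, and attribution could run in either direction.
- **Every late AE is dropped unless related.** All SAEs are kept to EOS.
- **The tables run past the period that the protocol assesses.** Section 11.1 alone suggests this, but Sections 11.1.1 and 14.2.6.2 extend monitoring to EOS.
- **The answers at the call are thrown away.** Appendix 16.2.5.5 lists by subject whether any AE occurred since the last visit. An unrelated non-serious event simply does not become an AE record.

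**Conclusion.** The concern holds as a mismatch between collection and tabulation. From EOT/ET to EOS, unrelated non-serious events cannot appear, while SAP 7.3 combines what is recorded there with the earlier all-cause events and gives no end date. The combination follows from the missing end date and is not an explicit SAP statement. All-cause TEAE counts to EOS are therefore understated, and the Related/Not Related counts are tilted.

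The illustrative size, a true 50% appearing as 67% with 75% of events captured, rests on constant event rates and a 7-day gap to the call. The practical effect is probably small: a single dose, about 0.8% of drug left at EOT, up to 8 subjects per RI cohort, and descriptive safety analysis only. A difference by cohort remains a possibility and is not a finding. The change is still worth making because it is cheap and removes selection on an unblinded causality judgement.

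**What to change.** **If collection can still change:** amend Protocol 14.2.6.3 and footnote l so that every AE volunteered at the EOS call is recorded with its relationship, as SAEs already are. Align the wording on the call's purpose in the synopsis, Section 11.1.1, footnote e and SAP 3, and state in SAP 7.3 that the TEAE period runs to EOS. The call already asks an open question, and the investigator must already judge relatedness to apply the current rule. The cost is an amendment and a few more AE records among at most 48 subjects.

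**If it cannot:** the SAP file contains statistical output dated 30 April 2020, so collection may be over. In that case keep late related AEs and all SAEs in the tables, but show onset through EOT/ET separately from onset after it, with a footnote stating the capture rule. Onset dates and times are already in Appendix 16.2.7.1, so this needs a date condition and an extra panel. It does not recover unrecorded events, but it stops the counts from being read as all-cause to EOS.

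Ending the tables at EOT/ET would also remove the mixture. The price is that delayed related AEs and late SAEs, the late events that matter most for tolerability, would leave the frequency tables. The split is therefore preferable.

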14.2.6.4 Serious Adverse Event

If any AEs are serious, as defined by the FDA Code of Federal Regulations (CFR), Title 21, special procedures will be followed. All SAEs will be reported to the Sponsor or designee via fax or e-mail within 24 hours of first awareness of the event, whether or not the serious event(s) are deemed drug-related. All serious event reporting will adhere to 21 CFR 312.32 for Investigational New Drugs (IND) and to the Guidance for Industry and Investigators: Safety Reporting Requirements for INDs and BA/BE, dated December 2012. Any event that meets the criteria of a suspected unexpected serious adverse reaction (SUSAR) will be reported to the IRB/IEC according to site/CRU policy by the Investigator (or designee) and to regulatory authorities by the Sponsor (or Sponsor designee) according to regulatory authority requirements. Refer to Reference Safety Information (RSI) in the current IB for expected adverse reactions.

A SAE is any AE or suspected adverse reaction that in the view of either the PI (or designee) or Sponsor, results in any of the following outcomes: Death, a life-threatening AE, inpatient hospitalization or prolongation of existing hospitalization, a persistent or significant incapacity

or disability, or a congenital anomaly/birth defect. Important medical events that may not result in death, be life-threatening, or require hospitalization may be considered serious when, based upon appropriate medical judgment, they may jeopardize the patient or subject and may require medical or surgical intervention to prevent one of the outcomes listed in the above definition. Examples of such medical events include allergic bronchospasm requiring intensive treatment in an emergency room or at home, blood dyscrasias or convulsions that do not result in inpatient hospitalization, or the development of drug dependency or drug abuse.

Life-threatening is defined as an AE or suspected adverse reaction that in the view of the PI (or designee) or Sponsor, places the patient or subject at immediate risk of death. It does not include an AE or suspected adverse reaction that, had it occurred in a more severe form, might have caused death.

All SAEs must be reported on a SAE Report Form provided by Loxo Oncology and sent by fax or e-mail to the Sponsor listed in [Section 4](#) within 24 hours of first awareness of the event.

When using the SAE efax (+ 1 [contact]) a cover page including study identification number and study drug product (i.e., LOXO-292) is required. Alternatively, an email can be sent to [name].

The PI is not obligated to actively seek information regarding the occurrence of new SAEs beginning after EOS. However, if the PI learns of such an SAE, and that event is deemed associated with the use of study drug, he/she should promptly document and report the event.

The PI will be requested to supply detailed information as well as follow-up regarding the SAE. Although not considered an AE per se, the Sponsor must be notified of any subject or subject's partner who becomes pregnant during the study at any time between Screening until 90 days after study drug administration on Day 1.

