11.1.1 Confinement, Return Visits, and Follow-Up

Subjects will be housed in the CRU from Check-in (Day -1), at the time indicated by the CRU, until after completion of the Day 8 (EOT) or ET study procedures. EOT is defined as the day on which the subject is released from the CRU, following all study procedures (Study Events Flow Chart, [Section 7](#)).

At all times, a subject may be required to remain at the CRU for longer at the discretion of the PI or designee and/or Sponsor.

The CRU will contact subjects by phone call 7 days (\pm 2 days) after the EOT or ET visit (defined as EOS) to determine if an SAE or study drug related AE has occurred since the EOT or ET visit. All subjects who received LOXO-292 (including subjects who terminate the study early) will be contacted at EOS.

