12.1.1 All Subjects

1. Male or female (of non-childbearing potential only), 18-70 years of age, inclusive, at Screening.
2. Body mass index (BMI) ≥ 18.0 and $\leq 40.0 \text{ kg/m}^2$ at Screening and have a minimum weight of at least 50 kg at Screening.
3. Female of non-childbearing potential must have undergone one of the following sterilization procedures at least 6 months prior to dosing:
 - hysteroscopic sterilization;
 - bilateral tubal ligation or bilateral salpingectomy;
 - hysterectomy;
 - bilateral oophorectomy;

or be postmenopausal with amenorrhea for at least 1 year prior to dosing and follicle-stimulating hormone (FSH) serum levels consistent with postmenopausal status. Postmenopausal status will be confirmed with a screening serum follicle-stimulating hormone level value within the CRU's laboratory's expected range for post-menopausal status. All females must have a negative qualitative serum pregnancy test (serum human chorionic gonadotropin) at Screening and Check-in (Day -1).

4. Males who are capable of fathering a child must agree to use one of the following methods of contraception from the time of the dose administration through 6 months after the study drug administration on Day 1.

Male sterilization, with documented confirmation of surgical success. Male subjects will be surgically sterile for at least 90 days prior to Check-in (Day -1). If documentation is not available, male subjects must follow one of the contraception methods below:

- a. Male condom with spermicide, and
- b. For a female partner of male study participant:
 1. Intrauterine device (IUD) (hormonal IUD; e.g., Mirena[®]).
Copper IUDs are acceptable (e.g., ParaGard[®]);
 2. Established use of oral, implanted, transdermal, or hormonal method of contraception associated with inhibition of ovulation; or
 3. Bilateral tubal ligation.

Males who practice true abstinence because of a lifestyle choice (i.e., do not become abstinent just for the purpose of study participation) are exempt from contraceptive requirements. Periodic abstinence by a female partner (e.g., calendar, ovulation, symptothermal, postovulation methods) and withdrawal are not acceptable methods of contraception. If a male subject is abstinent at the time of signing the ICF but becomes sexually active during the study, he must agree to use contraception as described above.

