For male subjects, sexual intercourse with female partners who are pregnant or breastfeeding should be avoided unless condoms with spermicide are used from the time of the study drug administration until 6 months after study drug administration on Day 1. Male subjects are required to refrain from donation of sperm from Check-in (Day -1) until 6 months after study drug administration on Day 1.

For subjects who are exclusively in same-sex relationships, contraceptive requirements do not apply.

5. Understands the study procedures in the ICF, and be willing and able to comply with the protocol.

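### Pregnancy notification stops 90 days after dosing, but male precautions run to 6 months, leaving about 3 months in which a partner's pregnancy need not be notified

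*Protocol*

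**What the plan says.** All references are to the current protocol (Amendment 3).

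- **Notification.** Section 14.2.6.4 states that "the Sponsor must be notified of any subject or subject's partner who becomes pregnant during the study", and sets the period as "at any time between Screening until 90 days after study drug administration on Day 1".
- **Contraception.** Section 12.1.1, criterion 4, requires men who can father a child to use contraception "from the time of the dose administration through 6 months after the study drug administration on Day 1".
- **Pregnant or breastfeeding partner.** The same criterion permits intercourse with such a partner only on this condition: "condoms with spermicide are used from the time of the study drug administration until 6 months after study drug administration on Day 1".
- **Sperm donation.** "Male subjects are required to refrain from donation of sperm from Check-in (Day -1) until 6 months after study drug administration on Day 1".
- **After End of Study.** Section 14.2.6.4 adds: "The PI is not obligated to actively seek information regarding the occurrence of new SAEs beginning after EOS". If the investigator does learn of a later serious event and considers it drug-associated, it must be reported.

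The protocol gives no reason for the 90 days and does not define one at-risk period covering both rules. The SAP's safety section has no provision for pregnancy.

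**The concern.** Both periods are counted from the same single dose, yet one is about twice as long as the other. The protocol considers precautions necessary for 6 months. A partner's pregnancy in that period means that a precaution failed or was not followed, and a notification rule exists to capture exactly that. From about day 91 to month 6, a site that knows of such a pregnancy has no duty to pass it on.

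What is at stake is the completeness of safety information. The drug exposure comparison, the sample size and the statistical analyses do not depend on it.

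**Working it through.** The 90 days is a stated rule and is not derived from other inputs, so there is no plan figure to reproduce. The check compares two periods that share a starting point.

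**Length of the precaution period.** Adding 6 calendar months to every possible dosing date in 2019 gives 181 to 184 days.

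**Uncovered period** = precaution period − notification period after dosing:

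- shortest: 181 − 90 = 91 days
- longest: 184 − 90 = 94 days

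Notification therefore covers 90/184 = 49% to 90/181 = 50% of the days on which precautions apply. This is a share of days, not of risk.

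**Who is affected.** Section 12.1.1, criterion 1, admits only women of non-childbearing potential. In practice the gap concerns partners of male subjects.

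**Whether another rule closes the gap.**

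1. Section 14.2.6.4 says pregnancy is not in itself an adverse event, so adverse event reporting does not capture it.
2. Scheduled contact ends early. Section 11.1.1: "The CRU will contact subjects by phone call 7 days" (± 2 days) after discharge or early termination. A completer is discharged on Day 8, which is 7 days after dosing, so the call falls 7 + 7 ± 2 = 12 to 16 days after dosing. That is Day 13 to Day 17, nominally Day 15.
3. After that call, only serious events that the investigator happens to learn of and judges drug-associated are reportable. A congenital anomaly is in the serious event definition and could qualify; the pregnancy itself would not.

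**After the change.** With notification extended to 6 months the uncovered period is 0 days.

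**The case against.** The strongest reply is that no rule is broken. Precautions for men and a duty to notify are different things, nothing in the documents says they must last equally long, and a sponsor may reasonably set precautions more cautiously than notification. The original protocol already paired 90 days with 6 months. Amendment 2 moved the starting point of the 90 days to Day 1 and revised the male contraception text while leaving the lengths unchanged. That history shows neither intent nor oversight.

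The biological argument is also fair. With a half-life of about 24 hours (Section 9.1.1), day 90 is about 90 half-lives after the only dose. If renal impairment lengthened the half-life fourfold (an assumption), it would still be 90/4 = 22.5 half-lives. Section 9.1.1 also reports negative bacterial mutation and in vitro genotoxicity results. These do not exclude every effect through the father, but a pregnancy in the gap is unlikely to say much about the drug. The number of men concerned is also below the 48-subject ceiling, because documented-sterile men, true abstainers and men exclusively in same-sex relationships fall outside the contraception requirement.

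Two further points concern the remedy. Extending the period finds no extra pregnancies, because no contact is scheduled after about Day 15. And the sentence speaks of pregnancies during the study, which, read literally, could end at the follow-up call. The first point stands. The second does not defeat the change: the sentence gives an explicit end date, which governs, and the literal reading would make the covered period shorter still.

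These arguments keep the priority low. They do not explain why precautions are required for a period in which their failure need not be notified.

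**Conclusion.** The point holds as a low-priority alignment of safety reporting. Notification ends 91 to 94 days before the male precautions do, and no section of the documents reviewed fills the interval. The serious event route is a passive, partial backstop that does not cover a pregnancy as such.

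Few events are expected, and the consequence is limited to pregnancies that a site already knows about. The textual mismatch is certain. Its practical effect is less so, because the consent and pregnancy report forms were not available and might set a longer period.

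**What to change.** In the pregnancy sentence of Section 14.2.6.4, change the end of the notification period from 90 days to 6 months after study drug administration on Day 1. Check that the consent form and the pregnancy report form use the same period.

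The cost is one phrase in the protocol. It needs no added visits, calls, samples or subjects. The only burden is that sites carry a passive reporting duty for about three months longer. If the sponsor believes that risk has ended by 90 days, the alternative is to state that reasoning and explain why precautions continue beyond it.
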